### **12. Local Number of Participants**

*The total number of participants to be accrued locally is 100.*

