### Protection against Risks

We will follow safeguards to minimize the risk to our subjects: a) we will carefully monitor capillary BG at the bedside using a hand-held glucose meter, b) only experienced nurses/or phlebotomist will draw blood samples. To prevent significant clinical events, no patients with history of significant liver, renal impairment or cardiac failure will be recruited in this study.

We expect that approximately 20-30% in insulin and sulfonylurea treated patients will experience one or more episodes of hypoglycemia. To minimize the risk of hypoglycemia, the starting dose will be adjusted following a protocol that has been shown effective on insulin adjustment. To avoid hypoglycemia, the total daily dose of insulin will be decreased by 10% for BG between 70-99 mg/dl and by 20% after each episode of hypoglycemia (BG < 70 mg/dl).

**CGM – alarms and hypoglycemia protocol.** We will use a Dexcom CGM device with a modified transmitter able to store and transmit glucose data to different devices including a notebook/IPAD or computer desk located at the nursing station. The use of hypoglycemia alarm set at 85 mg/dl will alert nursing staff and providers that a patient maybe at risk of hypoglycemia. If this occurs, the nursing staff will meet patient in the room to assess clinical status and signs/symptoms of hypoglycemia and will perform a POC glucose testing to confirm glucose values. In addition, a carbohydrate load of 15 grams will be provided to patients as per hospital protocol to avoid hypoglycemia.

**Hyperglycemia alarm** will be set at 300 mg/dl to alert the nursing staff and providers of the risk of clinically significant hyperglycemic complication. If this occurs, the nursing staff will meet patient in the room to assess clinical status and will perform a POC glucose testing to confirm glucose values. If BG > 300 mg/dl, nursing staff will communicate this high glucose value to the primary care team. The primary care team will review patient record and insulin administration prior to determining need for additional corrective rapid-acting insulin. If patient has received corrective insulin within the past 2 hours, additional correction will not be given, and the blood

sugar will be re-checked in 1 hour. If the glucose value continues to rise with a rise indicated by CGM trend arrow, then additional corrective insulin will be given at that time.

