The present aims of this RCT is to investigate whether the Dexcom G6 CGM with Glucose Telemetry System (CGM-GTS) with hypoglycemia alarm may reduce the risk of hypoglycemia < 70 mg/dl (safety outcome) and improve glycemic control as measured by the percent of time in range (TIR) 70-180 mg/dl (efficacy end-point) in patients with T2D in subacute and long-term skilled nursing care facilities. Patients in the standard of care group will wear a blinded CGM and receive POC testing before meals and bedtime, with providers adjusting oral agents or insulin dose based on POC results. Patients in the intervention CGM group will have a single daily fasting POC testing and will wear a real-time Dexcom G6 with GTS, and providers will adjust oral or insulin therapy based on CGM-GTS profile information. [name], PhD at the School of Public Health at Emory University will conduct statistical analyses.

For the safety endpoint, we will first compare the proportions of patients who have at least one episode of hypoglycemia by POC and by CGM. We will first perform nonparametric comparisons of the rate of hypoglycemia based on a two-sided Chi-square test (or Fisher's exact test in the presence of low incidence rates), followed by the Cochran-Mantel-Haenszel test, which adjusts for the potential center effect. Then we will perform univariate Poisson regression (or Negative Binomial regression) to assess whether there is any difference in the number of clinically significant hypoglycemia events between the two treatment groups. We will further conduct multivariate Logistic regression, Poisson regression (or Negative Binomial regression) to estimate the difference in the rate and frequency of hypoglycemia while adjusting for potential confounders. A glucose value < 70 mg/dl is considered as hypoglycemia requiring a nurse-driven response; thus, a BG <70 mg/dl will be used for sample size calculation. Data from Singh et al a reduction of hypoglycemia was reported comparing the CGM/GTS system than POC (Singh et al 2020) per patient (0.67 episodes per patient, 95% CI 0.34-1.30

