versus 1.69 episodes per patient, 95% CI 1.11-2.58,  $p= 0.024$ ) . Based on the results of the recent glargine U100 vs U300 study using CGM monitoring in the hospital, 56% had CGM BG readings <70 mg/dl (vs 14% with POC testing-standard of care), it is reasonable to assume 60% of resident on LTC facilities will experience one or more BG < 70 mg/dl by CGM. If we assume that 35% in the standard of care group will have at least one BG <70 mg/dl (based on linagliptin LTC study) , using one-sided, two-sample t-tests, we require we will need 70 patients per group to achieve 80% power.

Hypoglycemia incidence, Rate in the CGM intervention group	30%	35%	40%	45%	50%
Estimated sample size (N/group) for 80% power	49	70	107	186	407

For the efficacy endpoint, we will compare mean daily glucose levels measured by CGM or POC, and percent TIR measured by CGM between treatment groups by nonparametric Wilcoxon-tests or two-sample t-tests, and by multivariate linear regression, which adjusts for other potential confounders such as age, gender, BMI, center, and admission HbA1c. A logarithm transformation may be employed to make the data better conform to the normality assumption. When conducting multivariate regression analyses, we will apply standard variable selection and model checking procedures to decide the final model. Stepwise, backward, or forward model selection strategy will be adopted to determine the variables to be included in the final model. Standard diagnostic and model checking procedures, such as deviance residual plot and Hosmer- Lemeshow test, will be applied to examine the fit of the developed models. To show non-inferiority between POC and CGM in terms of glycemic control, we set the equivalence margin of 18 mg/dl (1 mosm/l), from a view that a difference <18 mg/dl is usually not considered as clinically significant . Based on the results from our recent CGM trials , it is reasonable to assume the standard deviation of mean daily BG is bounded above by 45 mg/dl. Assuming the true BG difference between the treatment groups is zero, and using one-sided, two-sample t-tests, we require 70 subjects for each treatment group to achieve 80% power.

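### The plan enrols 100 but its own calculation asks for 140; at 50 per arm the planned test has about 73% power, not 80%, and the assumed rates and test are stated inconsistently

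*Combined protocol and SAP*

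**What the plan says.** **Size.** The summary table in section 1 gives a sample size of 100. Section 12 agrees: "The total number of participants to be accrued locally is 100".

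**Hypoglycemia calculation (section 18, Data management and statistical analysis).** The text takes 60% of residents as having at least one value below 70 mg/dl by CGM, without naming an arm. It continues "If we assume that 35% in the standard of care group will have at least one BG <70 mg/dl", citing the linagliptin long-term care trial, and concludes "using one-sided, two-sample t-tests, we require we will need 70 patients per group to achieve 80% power". The table that follows is headed "Hypoglycemia incidence, Rate in the CGM intervention group". It lists 49, 70, 107, 186 and 407 per group for rates of 30%, 35%, 40%, 45% and 50%. No alpha and no allocation ratio are stated.

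**Planned analysis (same section).** The first step is to "compare the proportions of patients who have at least one episode of hypoglycemia by POC and by CGM", using "nonparametric comparisons of the rate of hypoglycemia based on a two-sided Chi-square test", or Fisher's exact test where incidence is low.

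**Mean daily glucose (same section).** A non-inferiority calculation uses a margin of 18 mg/dl, a true difference of zero and one-sided t-tests, and says "it is reasonable to assume the standard deviation of mean daily BG is bounded above by 45 mg/dl". It again arrives at 70 per group for 80% power.

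**Elsewhere.** Section 15, Protection against Risks: "We expect that approximately 20-30% in insulin and sulfonylurea treated patients will experience one or more episodes of hypoglycemia". It names no arm and no measurement method.

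**The concern.** Enrolling 100 cannot meet a requirement of 70 per group, and the document says nothing about why the smaller number is enough. Three elements of the hypoglycemia calculation are also uncertain.

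- **Direction.** If the text is read literally, with 35% in standard of care and 60% left for CGM-GTS, hypoglycemia rises under the intervention. That reverses the aim of the trial.
- **Test.** A one-sided t-test is named for a yes/no outcome that will be analysed with a two-sided chi-square.
- **Measurement.** The 60% is a CGM rate. The 35% is attributed to a trial that section 3 describes as measuring glucose before meals. The two methods can differ widely: section 18 itself quotes 56% by CGM against 14% by POC in one hospital study.

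What is at stake is the reading of a primary endpoint. If the trial finds no difference, nobody could say from the protocol what difference it was built to detect, or with what probability.

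**Working it through.** **Inputs.** From section 18: rates of 60% and 35%, power 80%, margin 18 mg/dl, SD bound 45 mg/dl, true difference 0. From sections 1 and 12: N = 100. Assumed because not stated: alpha 0.05 and 1:1 allocation, so 50 per arm.

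**Step 1. Reproduce the plan's 70.** The uncorrected two-proportion formula at two-sided 5% is

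n = [1.960·√(2·p̄·(1−p̄)) + 0.842·√(p₁(1−p₁) + p₂(1−p₂))]² / (p₁−p₂)².

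With p₁ = 0.60, p₂ = 0.35 and p̄ = 0.475:

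n = [1.960·√0.49875 + 0.842·√0.4675]² / 0.0625 = 61.4.

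The continuity correction is n′ = (n/4)·[1 + √(1 + 4/(n·|p₁−p₂|))]², which gives (61.4/4)·[1 + √(1 + 4/15.36)]² = 69.2, so 70.

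The whole table, always against 60%:

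| Rate | Plan | Two-sided 5%, corrected | Two-sided 5%, uncorrected | One-sided 5% t-test | One-sided 2.5% t-test |
|---|---|---|---|---|---|
| 30% | 49 | 48.4 | 42.0 | 32 | 41 |
| 35% | 70 | 69.2 | 61.4 | 47 | 60 |
| 40% | 107 | 106.7 | 96.9 | 75 | 96 |
| 45% | 186 | 185.9 | 172.8 | 135 | 172 |
| 50% | 407 | 407.1 | 387.3 | 304 | 386 |

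Only the corrected two-sided column fits (one-sided 2.5% is the same calculation). So 70 is a sound number for 60% versus 35%; the description of the test is what fails. The match also points to 60% as the comparator and to the listed rates as those of the CGM arm. This is inferred from the figures; the document does not state it.

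**Step 2. Power for 60% versus 35%.** Exact binomial enumeration, alpha 0.05:

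| Per arm | Two-sided chi-square | Continuity-corrected | One-sided, uncorrected |
|---|---|---|---|
| 50 | 73.4% | 66.3% | 79.9% |
| 70 | 85.3% | 80.9% | 91.8% |

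Fisher's exact test gives the same 66.3% at 50 per arm and 80.9% at 70. The normal approximation for the chi-square at 50 per arm is 71.3%. With a 40:60 split the exact figure is 71%. Searching upwards from 45 per arm, 80% is first reached at 60 per arm (chi-square) or 70 (corrected).

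**Step 3. Sensitivity to the CGM-arm rate, 50 per arm.** At 30%, power is 87.6% (82.9% corrected); at 40%, 54.3% (46.2%). Power of 80% needs a rate of about 33% (31% corrected).

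**Step 4. Non-inferiority on mean daily glucose.** The normal approximation at one-sided 5% is n = 2·(45/18)²·(1.645 + 0.842)² = 12.5 × 6.18 = 77.3, so 78 per group; the noncentral t also gives 78. Power by noncentral t at SD 45 is 76.1% at 70 per group and 63.4% at 50. At one-sided 2.5% these become 65.2% and 50.8%. At one-sided 5%, 80% is reached at 70 per group if the SD is about 42.6 or less, and at 50 per group if it is about 35.9 or less.

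**The case against.** **A one-sided test nearly rescues 100.** With one-sided 5%, 50 per arm has 79.9% exact power. This is the best argument for the plan, and the arithmetic is right. But one-sided testing contradicts the planned two-sided chi-square, does not reproduce the table, and would make the plan's own 70 unnecessary. It shows that sidedness must be stated; the conflict remains.

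**The 30% column would fit 100.** It needs 49 per group, and section 15 expects 20–30% of residents to have hypoglycemia. However, the sample size text adopts 35% and 70, and the section 15 figure is tied to neither an arm nor a method.

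**The 100 might be only the local share.** Section 12 does say locally, but section 1 gives 100 as the study size and section 23 lists only Grady and Emory-affiliated facilities.

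**Quoting 73% against 80% mixes bases.** This is fair. Like for like, going from 70 to 50 per arm takes power from 85% to 73% without correction, or from 81% to 66% with it. The exact 73.4% also sits high on an uneven curve (73.0% at 54 per arm), so 71–73% is a safer description of the uncorrected test.

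**Attrition.** The 73% assumes 100 evaluable residents. Section 14 lets participants withdraw and have their data removed, and no allowance is stated. At 45 evaluable per arm the chi-square has 65% power. This makes the shortfall worse.

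**The SD of 45 is an upper bound.** True, so the non-inferiority figures are minimum values. The claim of 80% at 70 per group still fails at the bound the plan chose.

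**Conclusion.** The concern holds. The contradictions over N (100 against 140), over which arm has 35%, and between the stated and planned tests can be read directly from the document and need no assumption.

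The size of the shortfall rests on alpha 0.05, equal allocation and complete data. On that footing, the enrolment target gives about 73% power for 60% versus 35% with the planned test, and about 66% on the corrected basis that appears to lie behind the table. Both fall short of the stated 80%.

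Two secondary points also stand: the 60% and 35% appear to come from different measurement methods, and the non-inferiority calculation does not give 80% power at its own SD bound. The power of the planned Poisson or negative binomial models for event counts was not assessed.

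**What to change.** 1. State one N in sections 1, 12 and 18, with the allocation ratio, alpha and sidedness, and say whether N means enrolled or evaluable.
2. If 100 stands, restate the hypoglycemia power: with 50 evaluable per arm and a two-sided 5% chi-square, about 73% for 60% versus 35% (about 66% if continuity-corrected); 80% is reached at a CGM-GTS rate of about 33% (31% corrected).
3. Align the arm labels in text and table. The table and the trial's aim imply 60% for standard of care and 35% for CGM-GTS; the sponsor's statistician should confirm this.
4. Replace the t-test description for this endpoint with the method actually used for the table, confirmed by the statistician and consistent with the planned chi-square.
5. Say whether CGM or POC defines hypoglycemia for the sample size. Either source the 35% on that measurement or label it an assumption.
6. Restate the non-inferiority power: at one-sided 5% and an SD of at most 45 mg/dl, at least about 63% at 50 per arm, or at least 76% at 70.

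**Cost.** If 100 is kept, this is protocol wording only, and the stated power becomes less favourable. Keeping 70 per group instead means 140 − 100 = 40 more participants, and non-inferiority at SD 45 would still fall short of 80%.

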## 6. Procedures Involved

Residents with T2D in subacute and long-term skilled nursing care facilities treated with insulin and/or insulin-secretagogues will be randomized to a standard of care group with POC testing or to real time Dexcom CGM with GTS for up to 60 days of admission.

Patients in the standard of care group will wear a blinded CGM and receive POC testing before meals and bedtime, with providers adjusting oral agents or insulin dose based on POC results. Patients in the intervention CGM group will have a single daily fasting POC testing and will wear a real-time Dexcom G6 with GTS, and providers will adjust oral or insulin therapy based on CGM-GTS profile information.

Nursing staff and primary care will receive education on the CGM technology by our research team.

Education efforts will include general information on the technology, how and when to remove or replace CGM sensors and transmitters, and the hypoglycemia prevention protocol. Treatment of hypoglycemia (POC <70 mg/dl) will be similar in both groups following a standard hospital protocol.

[figure not shown]
CGM alarm settings, and prevention of hypoglycemia protocol. Hypoglycemia alarm will be set to < 85 mg/dl (for prevention for low blood glucose levels). Nursing staff will be instructed to provide 15 grams of carbohydrates in response to a hypoglycemia alarm. For control group (blinded CGM) CGM alarms are turned off, however if the POC is found to be between <80 mg/dl by POC, 15 grams of carbohydrates will be given as a preventive measurement for hypoglycemia (standard of care).

The hyperglycemia alarm will be set at 300 mg/dl. If this occurs, the nursing staff will assess clinical status and perform a POC glucose testing to confirm glucose values. If BG > 300 mg/dl, nursing staff will communicate the high glucose value to the primary care team.

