### Inclusion Criteria:

1. Males and females admitted to subacute and long-term skilled nursing care facilities
2. Known history of T2D treated with insulin (glargine, detemir, degludec, NPH, premixed insulin) or sliding scale regular insulin) or insulin secretagogues (sulfonylureas, repaglinide, nateglinide) with or without additional oral antidiabetic agents (alpha-glucosidase inhibitors, thiazolidinedione, SGLT2- inhibitors, DPP4-inhibitors), short- and long-acting GLP1-RA (exenatide, liraglutide, dulaglutide, semaglutide)
3. Patients with an expected LTC length-of-stay > 1 week

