## 19. Provisions to Monitor the Data to Ensure the Safety of Participants

Baseline and daily information will be entered by the study coordinators into data collection paper forms and into an electronic database (REDCap) provided by the Emory Research Information Technology Department. Baseline data will include demographics/history form (subject gender, age, ethnicity, type of treatment and comorbid conditions, body weight, BMI, laboratory results). Daily information will be collected on treatment, nutrition, blood glucose and laboratory values, complications and adverse events (hypoglycemia). The safety of interventions and treatments associated with this protocol will be under continuous review by

the investigative team. All adverse events will be reviewed bi-weekly in a multidisciplinary format that will involve review by a physician, and other members of the research team. All Serious Adverse Events will be reviewed within the applicable guidelines and submitted to the IRB and other appropriate regulatory bodies governing this study.

In addition, we have implemented protection against risks approaches as above to minimize the risk to our subjects.

**Stopping Rules:** We plan to perform interim analysis on the primary endpoint every 6 months and/or when half of the subjects have been randomized. The trial will be stopped if there is evidence beyond a reasonable doubt of a difference in the rate of death and hospital complications (two-sided alpha level, <0.01) between the treatment groups.

Plans for transmission of temporary or permanent suspension actions:

Any actions that mandate temporary or permanent suspension of study will be transmitted to the Emory IRB, and, if appropriate, to the FDA.

The frequency of protocol review will be: every 6 months.

The PI will forward reports of safety reviews within 15 days of the meeting to the Emory IRB.

See full Data safety monitoring plan in the attachment labeled Data Safety Monitoring Plan  
A Data Safety Monitoring Board or Safety Officer has been designated for this study.

[name]  
Department of Medicine/Endocrinology

[name], MPH  
Department of Medicine/Endocrinology

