### **24. Resources Available**

Potential subjects will be identified by their treating physicians and referred to the researchers. Residents' private and identifiable information will not be shared prior to receiving permission from the resident to do so. All residents with history of diabetes will be considered for participation. The research team and/or the research coordinators will also review resident's medical records and laboratory tests to identify potential candidates. Once identified, the investigators and/or research coordinators will discuss the protocol with the attending physician taking care of the resident and request permission to include him/her in the trial. If the primary physician agrees to include the resident in the trial, then the resident will be invited to participate in the study. Potential candidates will be informed that there are other forms for glucose monitoring available to manage their diabetes. Long-term care residents will be instructed both verbally and in the written informed consent form that their participation in the study is entirely voluntary and that they can withdraw at any time, which will in no way compromise or alter the usual care that they would otherwise receive. They will also be given the phone numbers of the PI, IRB chair and Grady official to whom they can address any questions or concerns.

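### The only named glycaemic covariate, admission HbA1c, has no date window and may be old or absent for long-stay residents; a dated baseline from the chart would make the adjusted analyses more precise

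*Combined protocol and SAP*

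**What the plan says.** **Efficacy model.** Section 18 (Data management and statistical analysis) compares mean daily glucose and time in range (TIR) by Wilcoxon or t-test, then by a linear regression "which adjusts for other potential confounders such as age, gender, BMI, center, and admission HbA1c". The list is open, but admission HbA1c is its only glycaemic entry. No date window is attached, and stepwise, backward or forward selection decides which variables stay.

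**Hypoglycemia models.** The same section uses logistic and Poisson or negative binomial regression "to estimate the difference in the rate and frequency of hypoglycemia while adjusting for potential confounders". No covariate is named.

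**Data collected.** Section 19 states: "Baseline data will include demographics/history form (subject gender, age, ethnicity, type of treatment and comorbid conditions, body weight, BMI, laboratory results". Which laboratory tests, and from when, is not said. Glucose is named only among daily items: "Daily information will be collected on treatment, nutrition, blood glucose and laboratory values, complications and adverse events (hypoglycemia".

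**Who can enter.** The only stay criterion in Section 10 is "Patients with an expected LTC length-of-stay > 1 week". Section 24 adds "All residents with history of diabetes will be considered for participation", and there is no maximum time from admission to randomisation. Section 24 also says that research staff "will also review resident's medical records and laboratory tests to identify potential candidates".

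**Usual monitoring.** Sections 3 and 4 describe POC testing before meals and at bedtime as the usual or recommended practice.

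**The concern.** Admission is a natural time anchor in a hospital trial. The sponsor's hospital cohort with the same sensor had a median stay of 5 days (Section 3, preliminary results), so an admission HbA1c was current when the study began. In this trial, subacute and long-term residents are both eligible. For a recent subacute admission the covariate is sound. For someone admitted a year or more earlier it may say little about glycaemia at randomisation, or may never have been measured. The plan gives no rule for a missing covariate.

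Recent glucose and recent hypoglycemia are the obvious candidate predictors of on-study glucose and new hypoglycemia. Section 6 describes no stratification of the randomisation, and the Cochran-Mantel-Haenszel test adjusts for center only. The regressions are therefore the only planned route to adjust for a chance glycaemic difference between arms. If their one glycaemic covariate is stale, they gain little precision, and a baseline table cannot show whether the arms were alike in glycaemia when randomised.

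**Working it through.** **1. Inputs.** From Section 18: non-inferiority margin 18 mg/dl, SD of mean daily BG 45 mg/dl (an upper bound), true difference 0, one-sided two-sample t-test. From the Study Summary and Section 12: 100 participants. Assumed because the documents do not say: 1:1 allocation (50 per group), one-sided alpha 0.05 (0.025 also shown), and the correlation r between the baseline measure and on-study mean glucose.

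**2. The plan's own figure.** Section 18 states 70 per group for 80% power. With n = 2 × [SD × (z for alpha + z for power) / margin]²:

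- alpha 0.05: 2 × [45 × (1.645 + 0.842) / 18]² = 77.3, so 78 per group;
- alpha 0.025: 2 × [45 × (1.960 + 0.842) / 18]² = 98.1, so 99 per group.

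The stated 70 does not reproduce at either level. At 70 per group and one-sided 0.05, power is 76%. That discrepancy, and the gap between 2 × 70 = 140 and the planned 100, are separate matters. The calculation below uses 50 per group.

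**3. What a baseline covariate buys.** Linear adjustment reduces the residual SD to 45 × √(1 − r²). At 50 per group the noncentrality is 18 / [45 × √(1 − r²) × √(2/50)] = 2 / √(1 − r²), referred to a t distribution with 98 degrees of freedom.

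| r (assumed) | Residual SD | Noncentrality | Power, one-sided 0.05 | Power, one-sided 0.025 |
|---|---|---|---|---|
| 0 | 45.0 | 2.00 | 63% | 51% |
| 0.3 | 42.9 | 2.10 | 67% | 55% |
| 0.5 | 39.0 | 2.31 | 74% | 63% |
| 0.6 | 36.0 | 2.50 | 80% | 70% |
| 0.7 | 32.1 | 2.80 | 87% | 79% |

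A weak covariate (r up to 0.3) adds at most about 4 points of power. One at 0.5 to 0.7 adds about 11 to 28 points, depending on alpha. Where an old admission HbA1c or a current baseline would fall in this table is not known from the documents.

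**4. Bias.** In 20,000 simulated trials with 50 per group and no baseline adjustment, at r of 0.3, 0.6 and 0.8, the mean error in the difference was below 0.1 mg/dl. Type I error was 4.9% to 5.3% at a nominal 5%. An unused or stale baseline does not distort the randomised comparison.

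**5. Where the arithmetic stops.** The √(1 − r²) formula belongs to a linear model. It does not apply to the chi-square or logistic analysis of any hypoglycemia. For TIR the documents give no SD, so no power figure is offered there either.

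**The case against.** Three stronger readings are tempting, and the documents support none of them.

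- **That neither primary endpoint has a valid baseline.** Section 4 defines both primary outcomes as differences between the randomised groups during admission, not as changes from baseline. Section 18 tests them first without baseline adjustment. Randomisation makes that comparison valid, as step 4 confirms, and its standard error already allows for chance imbalance.
- **That no pre-randomisation glucose is collected.** Section 19 is unspecific rather than exclusive: its baseline items include laboratory results, and the form itself is not shown. Staff already review charts at screening, and the covariate list is open-ended. The accurate statement is that no such covariate is specified.
- **That long-stay residents would have no study time.** Section 6 says participants "will be randomized to a standard of care group with POC testing or to real time Dexcom CGM with GTS for up to 60 days" and counts those days as days of admission, so a reader might infer that someone resident for 60 days has none left. The Study Summary and Section 9 give 60 days as a limit on the individual's participation, which cannot start before enrolment.

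Further limits on the point also stand. The correlations are assumed. The share of long-stay residents is not given, so the trial-wide loss cannot be stated. Dropping residents with no HbA1c would be a consequence only under complete-case analysis, which the plan does not state. Chart POC is an imperfect baseline for hypoglycemia: Section 3 says POC misses about 40% of cases, and Section 18 cites 14% by POC against 56% by CGM.

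What the objection does not remove is that the plan names one glycaemic covariate, leaves it undated in a population with no limit on prior stay, and passes over chart data that should already exist under the usual monitoring it describes.

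**Conclusion.** The point holds as one of precision and specification; the validity of the trial is not in question. Admission HbA1c is undated and can be old or missing for long-stay residents, no pre-randomisation glucose covariate is specified, and the hypoglycemia models name none.

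For mean glucose, at the planned 100 participants and one-sided 0.05, the possible gain runs from about 63% power with no useful covariate to 74% at r = 0.5 and 87% at r = 0.7. This rests on assumed correlations, 1:1 allocation and the plan's upper-bound SD. No size can be put on TIR or on the hypoglycemia endpoint from the documents. The change is worth making because it costs little and would also let the report show glycaemic balance at randomisation.

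**What to change.** 1. In Section 18, replace admission HbA1c with baseline HbA1c, defined as the most recent value in a fixed window before randomisation (for example 90 days).
2. Add to the Section 19 baseline form, extracted from the existing chart in both arms, mean POC BG and whether any POC BG was below 70 mg/dl over a fixed pre-randomisation period (for example 7 days, or since admission if shorter).
3. Prespecify mean POC BG as a covariate for TIR and mean glucose. Enter the dated HbA1c, where available, as a separate covariate with a simple stated rule for missing values. The two are on different scales and should not stand in for each other.
4. Prespecify prior POC BG below 70 mg/dl as a covariate in the hypoglycemia models, noting that POC under-detects hypoglycemia and the gain there may be smaller.
5. Keep these covariates in the models rather than leaving them to variable selection.

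The window lengths are suggestions; what matters is that they are fixed in advance. The cost is two or three chart-extracted fields and some rewording, with no new blood draw and no change to treatment.
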